Data analysis:	
In this study, both patients and eyes will be considered as the analysis unit. Baseline characteristics will be summarized using descriptive statistics. For continuous variables, the mean, standard deviation, median and range will be presented. For categorical variables frequency and proportion will be used. Variables are identified and calculated at the index diagnosis and throughout the follow-up period for primary outcomes like VA.
 
In the progression analysis, the population will be restricted to patients with a minimum follow-up time (i.e. multiple visits at least one year apart, at least two years), or patients with valid VA reading at the index diagnosis and a second follow-up timepoint. [REDACTED]
 
The analysis of incident and prevalent calculations will use as the denominator, all patients referred to the retinal specialist. The proportion of patients with a GA diagnosis referred to the retinal specialist will be put into perspective by comparing to other conditions, such as proportion of patients referred to the retinal specialist with a diabetic macular edema (DME) diagnosis, or with a diabetic retinopathy (DR) diagnosis etc. Additionally, extrapolations will be done to approximate to a population-based estimate.
									
Milestones:	
 
 Start of data collection	05/2023		
 
 End of data collection	06/2023		
 
 Final report of study results	06/2023		
 
	Start of data collection	05/2023		End of data collection	06/2023		Final report of study results	06/2023	
Start of data collection	05/2023									
End of data collection	06/2023									
Final report of study results	06/2023									

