8. RESEARCH QUESTION AND OBJECTIVES

Research Question

To quantify and describe patients with a GA diagnosis in at least one eye. [REDACTED]

Primary objectives

To describe the characteristics* of patients with GA in at least one eye.

To describe characteristics* of the study eye and the fellow eye, at index diagnosis

To evaluate and characterize the progression of newly diagnosed patients with GA during each year for 5-year follow-up period. In particular, to describe patients' characteristics, study eye and the fellow eye characteristics over the 5-years follow up. [REDACTED]

Secondary objectives

To determine the first time occurrence of GA in the study eye, during the study period.

To determine the proportion of patients with GA in the study eye, over the study period.

To compare the GA first time occurrence and the proportion of GA, relative to other retinal conditions, and relative to proportion of retinal specialist contributing to [REDACTED] and the overall US retinal specialist.

To evaluate patients' management (i.e. patients visits and procedures) over the study period.

To describe [REDACTED]

the overall GA population.

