9. RESEARCH METHODS

9.1 STUDY DESIGN

This is an observational cohort study based on existing data.

BOEHRINGER INGELHEIM Group of Companies**NIS Protocol Template****Study number: 1484.0014****Page 12 of 30****Document number: <insert>****9.1.1 Study population**

Study inclusion criteria: All patients ≥ 50 years, with a GA diagnosis in at least one eye, including in the [REDACTED] database identified during the study period (January 2015 to April 2023).

Exclusion criteria: Patients without the information of laterality will be excluded.

No other exclusion criteria are applied for the identification of the study population and description of the patients and eye at baseline.

Additional note:

For certain analysis the patient population will be restricted to those with at least 12, 24, 36, 48, or 60 months of history following diagnosis of GA. For the analysis requiring a VA reading, a restriction to those patients with valid VA readings at the index diagnosis and the respective follow-up times will be applied.

For analysis estimating the size of the GA population relative to other retinal diseases, the same timeframe requirements that the study population will be applied. In this population, any patient in the database will be eligible, and the diagnosis of DME, DR or other conditions may be used for subgroup comparisons.

Primary Disease Definitions

In the [REDACTED] Database, retinal and other diseases are identified using the International Classification of Diseases (ICD), Tenth Revision, Clinical Modification. ICD 10 codes were launched in the USA in October 2015, and are the only version of ICD codes with adequate descriptions of GA and dry AMD severity. As such, only ICD 10 codes will be analyzed in this study and the study period defined above is directly related to the launch of ICD 10 plus a small buffer allowing for physician familiarity.

These codes are entered by the physician at patient visit, with an associated laterality. This, along with the ICD 10 laterality is used in combination to confirm in which eye the disease is occurring. For this study, a patient eye will be considered to have the study disease so long as there is an accompanying ICD code. The primary study diseases to be analyzed are dry AMD, GA and wAMD, and will be identified using the ICD codes in Table 1 below.

Table 1. Study disease definitions-codes.

Study Disease Definitions			
	Dry AMD*	Dry AMD with GA*	wAMD*

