9.7 DATA ANALYSIS

9.7.1 Main analysis

All analysis will be performed individually on the study population(s). All study results will be provided in tables, and key findings will be highlighted and summarized. The analyses will be conducted at both the patient and patient eye level, as appropriate.

Analysis for objective:

To describe the characteristics* of patients with GA in at least one eye.

To describe characteristics* of the study eye and the fellow eye, at index diagnosis (i.e., proportion of patients with GA in the fellow eye, [REDACTED]

All demographics, and clinical characteristics will be summarized at the index diagnosis date (first diagnosis of GA in the study eye).

Characteristics include demographics, comorbidities, comedications (patient level).

And at eye level; AMD, GA, eCNV, other ocular comorbidities, functional parameters i.e. VA. As well as treatments administered prior to or at index.

Summary will include descriptive statistics; continuous variables will consist of mean (SD) and median (IQR) while categorical variables will be described using frequency and proportion. Absolute numbers (n) of the variables (either yes or patients as appropriate) will be always included in the description of the results.

Analysis for objective:

To evaluate and characterize the progression of newly diagnosed patients with GA during a 5-year follow-up period. To describe patients' characteristics, study eye and the fellow eye characteristics, [REDACTED]

[REDACTED] or progression of the GA lesion in the study eye. To evaluate changes in VA, to evaluate changes in the lesion location, and lesion size (where available).

Patients with GA will be analyzed as an overall group. Subgroups will be also analyzed separately: only GA, GA and wAMD, GA and other comorbidities, and bilateral GA at baseline.

Ocular comorbidities will also be tracked longitudinally (yearly) from index date (GA diagnosis in the database) to better understand the disease journey.

Disease progression will be analyzed at both patient and each individual eye level.

Progression to dry AMD, to GA and to wAMD will be assessed independently using time to event analysis, and also the rate of progression that is seen in the study (2nd, 3rd, 4th, and 5th) years. Bilateral GA eyes at baseline will be evaluated for progression to wAMD

BOEHRINGER INGELHEIM Group of Companies**NIS Protocol Template****Study number: 1484.0014****Page 23 of 30****Document number: <insert>**

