For all time to event metrics, mean (SD), median and range will be summarized, while proportions will be summarized using N (%).

Kaplan Meier or Cox Hazard ratios may be applied when analyzing disease progression. Additionally, it will be determined how patients progress during the 1,2,3,4,5 years follow up according to the lesion location, and lesion size.

Analysis for objective:

To determine the occurrence of GA in the study eye during the study period (at the 12 (24, 36, 48, 60) month follow up period).

The calculation of the occurrence (new cases) of GA will be tracked against the overall number of patients included in the retinal specialist database (████████ database) in a time period (year) as the denominator initially.

The analysis to calculate the prevalent cases will include all patients with a GA diagnosis active in the database in the given time period in the numerator, and all patients included in the retinal specialist database (████████ database) will be used as the denominator initially.

Since, this analysis is referring to a population attending a retinal specialist during a given time period and therefore is not a general population-based estimates, in order to give a context to the data, the proportion of other common diagnosis in patients over 50 years or older attending the clinic in the same time period (e.g. diabetic macular edema, diabetic retinopathy, proliferative diabetic retinopathy, and wAMD) will be calculated. The denominator will be all patients attending to the retina specialist in the given time period using the age group category that is applicable in this study (50 years or older).

For the initial calculations, the look back period in 2015 will be used to discard patients with prevalence GA diagnosis in the subsequent years. prior diagnosis will be excluded and only new cases diagnosis in the time period will be considered in the numerator when calculating incidence.

The calculations will be conducted by calendar year, and absolute numbers (n) and correspondent percentage (%) will be provided. As a sub analysis, it will be evaluated if changes occurred after the third quarter of 2021, corresponding with the ██████████

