An additional analysis will be made to extrapolate the prevalent results to a national – US-level. For that analysis, the prevalence of GA will be considering all patients seen by a retina specialist in the given year. With this metric, estimation on a national level will be done using an estimation of all practicing US retina specialists.

When analyzing the rate of progression from dry AMD to GA, a conversion analysis will be done. This will include the overall rate of dry AMD eyes developing GA, along with a Kaplan Meier analysis assessing the rate of conversion over time. This analysis will track progression by month from diagnosis, censor any patient at the final visit in the database, and identify the incident GA diagnosis as an event.

Analysis for objectives:

To evaluate patients' management (i.e. patients visits and procedures) over the study period.

BOEHRINGER INGELHEIM Group of Companies**NIS Protocol Template****Page 24 of 30****Study number: 1484.0014****Document number: <insert>****Patients' management**

All visits, treatment, checkups, procedures, and other will be summarized across the duration of the study time frame as well as between the index diagnosis and at the 12 (24, 36, 48, 60) month follow up period.

An additional sub analysis will be conducted to evaluate the changes in the frequency of patients visits or procedures, checkups, after the third quarter of 2021 and after [REDACTED].

Summary will include descriptive statistics; continuous variables will be described by absolute numbers, the mean (SD), median and range, while categorical variables will be described using frequency and proportion. Absolute numbers (n), and correspondent percentage (%) of the variables (either eyes or patients as appropriate) will be always included in the description of the results.

Analysis for objective:

To describe and compare patients' characteristics in different progression subgroups (i.e. those that develop eCNV/those that not), of the overall GA population.

The following groups will be evaluated to better understand progression:

1. Patients that [REDACTED]

vs. those that do not in the 1, 2, 3, 4 and 5 years of follow up period.

2. Patients that [REDACTED]

vs. those that do not in the 1, 2, 3, 4 and 5 years of follow up period.

3. Patients with subfoveal lesion location vs. those with extrafoveal lesion location.

For this subgroup of patient's characteristics will be described and compared.

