Subgroups will be compared against one another to identify any differences in populations leading to progression. The characteristics will be extracted at the time of assignation to the group i.e. patient do not [REDACTED] in year one is contributing with his characteristics extracted at year 1 to the group (no progressors), that patient [REDACTED] at year 5 is contributing with his characteristics extracted at year 5 to the progressor group.

Summary will include descriptive statistics; continuous variables will be described by absolute numbers, the mean (SD), median and range, while categorical variables will be described using frequency and proportion. For discrete demographics or clinical characteristics, chi-squared test of proportion will be done to assess meaningful difference (standardized mean difference SMD may be used as an alternative), while continuous variables will be analyzed using SMD. Following univariate analysis on each metric, a multivariate logistic regression model will be run including relevant metrics identified in the univariate analysis.

Additional information on the analysis is described below:**Patient Demographics (at index and follow up):**

BOEHRINGER INGELHEIM Group of Companies**NIS Protocol Template****Page 25 of 30****Study number: 1484.0014****Document number: <insert>**

N (%); Age, gender, region; Bilateral status, other eye related diagnosis in study and fellow eye; Distribution by months of follow up; Concomitant illnesses (diabetes, cataract, etc.); Lesion location and size (along with % capture rate)

Progression : Progression of GA over time; Fellow eye AMD status; [REDACTED] (study and fellow eye) Mean (median/IQR) time to conversion; Conversion to GA (fellow eye) Mean (median/IQR) time to conversion; Proportion of patients with wAMD and GA (N, %)

[figure not shown]
Treatment Characteristics (follow up): Number of visits over time; Number of treatments over time, Mean (median) time to study treatment; Type of treatment – Anti-VEGF, Laser, Combination, Mean (median) time on therapy

New cases occurrence and prevalent cases of GA (stratified by index year): N (%)

- Age, gender
- Distribution by months of follow up
- Calculation to the % of patients attending the retinal specialist over the same time period for other retinal conditions i.e. wAMD, DR, dry AMD or DME.

Visual Acuity Outcomes

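### For progression after GA diagnosis, Kaplan-Meier/Cox is optional while mean time to conversion is required; that mean mainly tracks follow-up length, and the counting window for N (%) in the minimum-follow-up groups is not fixed

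*Combined protocol and SAP*

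**What the plan says.** Section 8 lists this among the primary objectives: "To evaluate and characterize the progression of newly diagnosed patients with GA during each year for 5-year follow-up period". Section 9.1.1 caps follow-up at 60 months from index.

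Section 9.7.1 treats the objective in three places:
- It makes a commitment: "Progression to dry AMD, to GA and to wAMD will be assessed independently using time to event analysis", together with progression rates for the second to fifth years. No estimator or censoring rule is named there.
- It then sets the required summary, "For all time to event metrics, mean (SD), median and range will be summarized, while proportions will be summarized using N" (%), followed by the conditional sentence "Kaplan Meier or Cox Hazard ratios may be applied when analyzing disease progression".
- The Progression output list at the end asks for "Conversion to GA (fellow eye) Mean (median/IQR) time to conversion". A partly redacted conversion item for both eyes has the same format. The visible list contains no cumulative-incidence output.

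For dry AMD to GA, the same section makes Kaplan-Meier definite: "This analysis will track progression by month from diagnosis, censor any patient at the final visit in the database", with the first GA diagnosis as the event.

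On populations, the abstract (section 4, Data analysis) says "In the progression analysis, the population will be restricted to patients with a minimum follow-up time", and section 9.1.1 says "For certain analysis the patient population will be restricted to those with at least 12, 24, 36, 48, or 60 months of history". Study Subgroups in section 9.2.1 writes the conversion horizons open-ended, from 1+ to 5+ years.

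On follow-up, section 9.5 gives an average of 22 months and 20,503 of 72,718 patients with visits after 3 years. Section 9.9 discloses the short follow-up and mentions Kaplan-Meier as a possible way to reduce bias, without committing to it.

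**The concern.** An analyst could carry out every mandatory instruction for this primary objective and never handle censoring. The required mean and SD need a conversion time, which a patient who has not converted does not have, so they describe observed converters only. When follow-up is short relative to the horizon, late conversions are mostly unseen. The mean among converters is then set largely by how long people were watched.

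Section 7 says the project is meant to clarify real-world conversion rates. Mean time to conversion is an easy figure to lift from a report, and a reader could take about 18 months as a property of the disease when it is mostly a property of the database.

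The percentages raise a separate point. If the 12+ month group may count conversions at any time, two analysts can report different N (%) for the same group, each within the text.

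**Working it through.** **Plan figures.** The documents give no event-rate, precision or power figure for progression, so there is nothing to reproduce. The two follow-up figures, 22 months (1.83 years, section 9.5) and 1.9 years (section 9.9), agree to rounding.

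**Inputs from the documents.** Feasibility period from 2016 (section 9.5), data to April 2023, so an entry window w = 88 months = 7.33 years. Patients with visits after 3 years: 20,503/72,718 = 28.2%. Average follow-up 22 months. Horizon 60 months.

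**Assumptions.** Uniform entry over w; exponential dropout at rate d; constant conversion hazard h of 3-15% per year (the documents give no yearly hazard); dropout unrelated to conversion.

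**Step 1: dropout.** The proportion with 36 months of potential follow-up is (88 − 36)/88 = 52/88 = 0.591.
- Fitting the 3-year figure: d = −ln(0.282/0.591)/3 = 0.247 per year, which implies a mean follow-up of 26.2 months.
- Fitting the 22-month mean: d = 0.349 per year, which implies 20.8% beyond 3 years.

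No single exponential fits both figures, so both rates are carried as a range.

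**Step 2: whole group.** Let SL(t) = exp(−d·t)·(1 − t/w), the probability of still being under follow-up at t. Then
- N (%) to 60 months = ∫₀⁵ h·exp(−h·t)·SL(t) dt
- mean among converters = ∫₀⁵ t·h·exp(−h·t)·SL(t) dt divided by the line above
- 5-year risk = 1 − exp(−5h)

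| h per year | 5-year risk | crude N (%), d = 0.247 / 0.349 | mean among converters, months, d = 0.247 / 0.349 |
|---|---|---|---|
| 3% | 13.9% | 6.0% / 5.1% | 19.1 / 17.3 |
| 5% | 22.1% | 9.6% / 8.3% | 18.7 / 16.9 |
| 10% | 39.3% | 17.9% / 15.5% | 17.8 / 16.2 |
| 15% | 52.8% | 24.9% / 21.7% | 17.0 / 15.4 |

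A five-fold hazard moves the mean by about 2 months. Crude N (%) rises about four-fold but is only 37-47% of the 5-year risk.

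**Step 3: effect of the follow-up group.** At a fixed 5% per year, with conversions counted to 60 months, the mean is 20.0 months (18.5 at higher dropout) in the 12+ group and 28.8 in the 60+ group. The disease is the same, and the group choice shifts the mean by 9-10 months.

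**Step 4: check without any dropout model.** With everyone followed for exactly T years, the mean among converters is 1/h − T·exp(−hT)/(1 − exp(−hT)). At T = 5:
- h = 3%: 33.33 − 30.90 = 2.44 years = 29.3 months
- h = 15%: 6.67 − 4.48 = 2.19 years = 26.3 months

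For 5-year risks of 10% and 40%, T = 12 to 60 months gives 6.0 to 29.5 and 5.9 to 27.5 months. The mean is about half the follow-up whatever the hazard.

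**Step 5: counting window.** In a group with at least T years of follow-up:
- conversions within T only: 1 − exp(−hT)
- all conversions to 60 months: 1 − exp(−hT) + ∫ from T to 5 of h·exp(−h·t)·SL(t)/SL(T) dt

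At h = 5%:
- 12+ group: 1 − exp(−0.05) = 4.9%, against 13.2% or 12.1%
- 36+ group: 1 − exp(−0.15) = 13.9%, against 19.1% or 18.7%

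**Step 6: Kaplan-Meier under the same assumptions.** Simulating 1,000,000 patients per setting gave 5-year estimates of 14.0%, 22.0-22.1% and 52.5-53.0% for hazards of 3%, 5% and 15%, against true risks of 13.9%, 22.1% and 52.8%. It recovers the truth because dropout was made uninformative.

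**The case against.** **The plan promises a time-to-event analysis.** Section 9.7.1 says so before it names Kaplan-Meier or Cox, so *may* could mean a choice between tools. Section 9.1.1 ends follow-up at the final visit, and section 9.9 removes lost patients from that point on. A reader might infer that the plan has no idea of censoring; the documents do not support that. What stands is that the mandatory sentence names uncensored summaries, the sentence naming the estimators is conditional, and section 9.9 is conditional too.

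**Horizons are given.** A reader might infer that no event window is stated anywhere. That is wrong. Section 9.1.1 gives yearly cut-offs to 60 months, and section 9.7.1 gives years 2 to 5 in one place and years 1 to 5 in others. For the progressor comparison it takes characteristics at the year of assignment, which implies that a year-5 event is not a year-1 progression. What stands is narrower: that rule is not visibly carried to N (%) in the 1+ to 5+ groups.

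**Parts of the text are redacted.** The redactions include the first primary-outcome bullet and part of the output list, and variable definitions sit in a separate file. Statements about what is missing therefore hold only for the visible text. The conditional Kaplan-Meier sentence itself is fully legible.

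**Slow and fast disease would not look alike.** A reader might infer that they would in the final report. They would not, because N (%) and yearly rates are also required and N (%) rises about four-fold across the assumed hazards. The insensitivity belongs to the mean time to conversion. The plan also separates groups by follow-up length, so a reader would know which group a mean came from.

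**The numbers are illustrative.** This is fair: hazards and dropout are assumed, and the plan does not say that means are taken over converters only. Non-converters have no conversion time, however, and using their follow-up time instead would tie the mean to follow-up even more closely.

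**Conclusion.** The concern holds in this form and should be fixed. For a primary objective, the estimator that handles censoring is optional, while a summary that mainly measures follow-up length is required.

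Over an assumed range of 3-15% per year, the required mean moves about 2 months in the whole group while the 5-year risk moves from 13.9% to 52.8%. That the mean follows follow-up length does not depend on the dropout model (step 4). The whole-group figures and the 37-47% capture by crude N (%) do, and they are illustrative.

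The minimum-follow-up groups are not biased in themselves. With conversions counted inside the fixed window, and retention unrelated to conversion, their percentages are valid. The visible text does not say that they are counted that way, and at 5% per year the difference in the 12+ group is 4.9% against 12.1-13.2%.

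Confidence is high on the Kaplan-Meier point and lower on what is absent, given the redactions. The study is not invalidated; its main progression output is underspecified.

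**What to change.** In section 9.7.1, change *may* to *will* and extend the dry AMD to GA method to each event-type endpoint after GA diagnosis as the main analysis:
- time from index, in eyes free of that endpoint at index, censored at the final visit;
- Kaplan-Meier estimates with 95% CI and numbers at risk at 12, 24, 36, 48 and 60 months.

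State that any median is either the Kaplan-Meier median or a median among converters. Label every mean (SD) time to conversion as among observed converters, descriptive only.

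Keep the minimum-follow-up groups as supporting analyses. Count N (%) in each within its own fixed window, and state the denominator.

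Restricted mean event-free time to 60 months is an optional addition. At 3% and 15% per year, (1 − exp(−5h))/h gives 55.7 and 42.2 months, so it separates the two hazards by 13.5 months.

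The cost is protocol wording and standard code in R, which is already the planned software; no new data are needed. Kaplan-Meier still assumes uninformative dropout, section 9.9 says deaths can be identified only as loss to follow-up, and the late intervals will be wider. The report should state these limits.

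### Section 9.7.1, read literally, puts GA on an all-age denominator and its comparators on a 50-or-older one, and the plan defines prevalent GA in conflicting ways

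*Combined protocol and SAP*

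**What the plan says.** **Age base**

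- Section 9.1.1 limits the GA study population to patients aged 50 or older.
- Section 9.7.1 has new GA cases "tracked against the overall number of patients included in the retinal specialist database" in a year. For prevalent GA it puts "all patients with a GA diagnosis active in the database in the given time period in the numerator" over all patients in the database. Both denominators are qualified by the word *initially*, and neither mentions age. The prevalence denominator also names no period, although the text goes on: "The calculations will be conducted by calendar year".
- The next paragraph of section 9.7.1 takes the proportions with diabetic macular edema (DME), diabetic retinopathy (DR), proliferative DR and wAMD among patients aged 50 or older. The denominator is attendees in the period, "using the age group category that is applicable in this study (50 years or older".
- Other descriptions of the same analysis give no age limit for any disease. The abstract (section 4) "will use as the denominator, all patients referred to the retinal specialist". The additional note in section 9.1.1, on the size of GA relative to other retinal diseases, says "any patient in the database will be eligible". The output list at the end of section 9.7.1 refers to the percentage "of patients attending the retinal specialist over the same time period for other retinal conditions". The US extrapolation in section 9.7.1 refers to patients seen in the year.

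**Prevalent GA**

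- Section 9.7.1 counts every patient with active GA in the period. Its exclusion of prior diagnoses applies only to incidence, and nothing removes new cases from prevalence.
- Section 9.3.2.1 counts as prevalent in a calendar year only those whose GA was diagnosed in an earlier year.
- Section 9.1.1 (Disease Status) works by eye and visit: every GA visit after the first one.
- Section 9.3.3.1 takes the first visit in the period for any study disease, provided it is not the first diagnosis.
- Section 9.9 describes prevalent cases as being seen over several years.

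**The concern.** Section 8 makes it a secondary objective to compare GA occurrence and the proportion with GA against other retinal conditions. That comparison is meaningful only if all diseases share one base. A GA numerator restricted to age 50 or older over an all-age denominator gives a smaller percentage than the same numerator over patients aged 50 or older. GA would then look less common than the comparators for a reason unrelated to disease.

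The prevalence definition matters in three places:

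- It sets the yearly prevalent count and percentage, and so the US figure built on the prevalent results.
- It decides whether a shift in new diagnoses after the third quarter of 2021, which section 9.7.1 plans to look for, shows in the same year's prevalence. It does under section 9.7.1 and does not under section 9.3.2.1.
- Section 9.9 argues that prevalent cases are less affected by earlier diagnosis elsewhere because they are followed over several years. That does not hold if first-year cases count as prevalent.

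The study is descriptive, so power and error rates are not affected. These proportions are themselves the result, and without a stated rule the choice could be made after the data are seen.

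**Working it through.** The plan gives no incidence or prevalence figure to reproduce. What follows sizes the two ambiguities.

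**1. Age base**

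Let *s* be the share of patients in the denominator who are 50 or older. The documents do not give it; 70-95% is assumed.

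- GA / all patients = (GA / patients aged 50 or older) × *s*.
- Each comparator is already on the 50-or-older base, so the ratio of GA to a comparator is multiplied by *s*, and GA is understated by 1 − *s*.
- *s* = 0.95: 5%. *s* = 0.90: 10%. *s* = 0.80: 20%. *s* = 0.70: 30%.
- If the 50-or-older sentence also governs GA: 0%.

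**2. Prevalence definition, if section 9.3.2.1 also requires a visit in the year**

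The two counts then differ by the patients first diagnosed in that year. Inputs from the feasibility table in section 9.5: 72,718 GA patients and 22 months mean follow-up. Assumptions: index dates spread evenly over the year, and a GA visit in every calendar year between first and last visit. A patient followed for *L* years then counts in about 1 + *L* calendar years under section 9.7.1 and *L* under section 9.3.2.1.

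- *L* = 22/12 = 1.83 years.
- Patient-years after the diagnosis year: 72,718 × 22/12 = 133,316.
- All active patient-years: 72,718 + 133,316 = 206,034.
- Share that are new cases: 72,718 / 206,034 = 35.3%.
- Ratio of the two counts: 206,034 / 133,316 = 1.55.

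Sensitivity of (1 + *L*)/*L*: 1.53 at the 1.9 years quoted in section 9.9, 2.0 at *L* = 1, 1.33 at *L* = 3. If 10-20% of the later years contain no visit, the later patient-years fall to 119,984-106,653 and the ratio rises to 1.61-1.68.

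**3. Prevalence definition, if section 9.3.2.1 does not require a visit**

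Assume even accrual from January 2016 to April 2023 (7.33 years; the feasibility table gives no end date).

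- New cases per year: 72,718 / 7.33 = about 9,916.
- Section 9.7.1 count in a year: 9,916 × (1 + 1.83) = about 28,096.
- Section 9.3.2.1 count for 2022, everyone diagnosed in 2016-2021: 9,916 × 6 = about 59,500.

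The ordering reverses, so the direction of the gap depends on an attendance rule that section 9.3.2.1 does not state.

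**The case against.** The strongest reply on the age base is that *initially* marks a provisional all-age denominator, and that the closing 50-or-older sentence, which invokes the age group of the study, sets the final one for every disease. That is a fair reading. However, the sentence sits in the paragraph on comparator diagnoses, after GA has been given its own denominators, and no later GA denominator is specified. The reading is possible but unstated.

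A reader might infer that the plan as a whole holds GA and the comparators to different age bases. The documents do not support that. The abstract, the note in section 9.1.1 and the output list leave age unstated for all diseases, and the abstract puts GA, DME and DR on the same base. The mismatch comes only from the literal reading of section 9.7.1.

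A reader might also infer that the two prevalence counts differ by exactly each year's new cases, and scale that gap by the 15-20% specialist coverage in section 9.2.1 into a US shortfall or excess. That too goes further than the text. It needs the attendance rule missing from section 9.3.2.1, although section 9.9 makes such a rule plausible by dropping patients once they are lost to follow-up. It also needs a scaling method that section 9.7.1 only sketches. The natural referent for the US figure is the prevalence calculation just before it, but this is not stated.

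Finally, section 9.3.2.1 identifies new and previously diagnosed patients separately, so their sum can be recovered from the counts. This limits the harm, but it does not say which count is the prevalence percentage.

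**Conclusion.** The point holds as a request to fix one base and one definition, and it is worth acting on before the analysis.

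- **Age base.** On the literal reading of section 9.7.1, GA is understated relative to the comparators by 5-30%, given an assumed 70-95% of patients aged 50 or older. On the alternative reading the effect is zero. The text does not settle which is meant.
- **Prevalence.** The conflict between section 9.7.1 and section 9.3.2.1 is in the text, and sections 9.1.1, 9.3.3.1 and 9.9 also sit badly with section 9.7.1. The ratio is roughly 1.5 if both counts require a visit in the year, with evenly spread index dates and yearly visits. Otherwise its size and direction are not fixed. The inputs come from a feasibility run that used ICD 10 codes plus exam notes, so study counts may differ.
- **Period.** The missing period in the prevalence denominator is a wording gap only, since the surrounding text points to calendar years.

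**What to change.** 1. Use one denominator for GA and all comparators: patients aged 50 or older with at least one visit in the calendar year. State it in sections 4, 9.1.1 and 9.7.1. An all-age base can stay as a secondary display.
2. Adopt one patient-level prevalence definition that requires a visit in the year. One suitable form is GA diagnosed in or before the year and seen in the year, with newly and previously diagnosed counts shown separately. Restricting to earlier-year diagnoses would also resolve the conflict, if used throughout.
3. Align sections 9.1.1 (Disease Status), 9.3.2.1, 9.3.3.1, 9.7.1 and 9.9 with that definition. Visit-level labels can stay if they are kept distinct from the patient-level count.
4. State that the US extrapolation uses the same count and base.

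The cost is wording and one age-and-year filter. No new data are needed, because the 50-or-older attending denominator is already planned for the comparators.
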